
4. To evaluate the safety of different investigational therapeutics as compared to the control arm as assessed by:
 
 • Cumulative incidence of SAEs through Day 29. • Cumulative incidence of Grade 3 and 4 clinical and/or laboratory AEs through Day 29. • Discontinuation or temporary suspension of study product administrations (for any reason) • Changes in complete blood count with differential, hemoglobin, platelets, creatinine, glucose, total bilirubin, alanine aminotransferase (ALT), aspartate aminotransferase (AST), and prothrombin time (PT) reported as international normalized ratio (INR) over time (analysis of lab values in addition to AEs noted above). 	
 • SAEs • Grade 3 and 4 AEs • Change in total WBC number, neutrophil number, lymphocyte number, hemoglobin, platelets, creatinine, glucose, total bilirubin, ALT, AST, and PT/INR from Day 1 to Days 2, 4, and 7 (while hospitalized); and Days 15 and 29 (if attends in-person visit or still hospitalized).
Exploratory	

1. To examine if the effect of convalescent plasma is associated with the days of symptoms at time of plasma administration
	
 • Plasma administered on day ≤ 7 vs. >7 days of symptoms on primary outcome

2. To examine if effect of convalescent plasma differs by comorbidities
	
 • Primary outcome in persons with ≤ 2 or ≥ 3 comorbidities (age ≥ 65 years, chronic lung, cardiac and renal disease, hypertension, diabetes, obesity and immunosuppression)

3. Research sample collection and management for future investigations:
 
Respiratory samples on days 1, 4, 7, 15, 29 and 30 mL of blood on days 1, 2, 4, 7 in hospital and days 15 and 29 in- or outpatient.
	
 • Sample Collection (Research lab draw with routine labs), preparation, labeling, shipping, storage and monitoring will be addressed in a future amendment.

4. Impact of donor convalescent plasma parameters on the activity of administered plasma
	
 • Donor plasma samples retained by Vitalant Blood services and provided to CURES-1 investigators will be tested for antibody levels, neutralization against SARS-CoV2, inflammatory and other mediators in relation to clinical and laboratory outcomes in study subjects.

World Health Organization (WHO) Ordinal Scale

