8.3.5 EXPLORATORY ASSESSMENTS

• To evaluate the impact of onset of symptoms relative to the time of plasma on the effect of convalescent plasma on primary outcome	Plasma administered on day ≤ 7 vs. >7 days of symptoms on primary outcome

• To evaluate the impact of comorbidity on the effect of convalescent plasma on primary outcome	Primary outcome in persons with ≤ 2 or ≥ 3 comorbidities (age ≥ 65 years, chronic lung, cardiac and renal disease, hypertension, diabetes, obesity and immunosuppression)

• To evaluate the relationship of clinical, immunologic, inflammatory, metabolic, coagulation, endocrinologic and microbiologic outcomes.	Using stored nasal swab fluid, plasma and blood cells, we will test for antibodies, antibody activity, cytokines, RNA transcripts and soluble and cellular markers of COVID-19 perturbations.

• Characterize the impact of specific parameters of convalescent plasma administered to subject on immunologic, inflammatory, metabolic, coagulation, and endocrinologic outcomes in study subjects.	Using samples of administered convalescent plasma, determine specific antibody levels, neutralization, cytokines and other soluble markers in relation to these outcomes in the plasma of study subjects and their outcomes.

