2.4.7 SUB-GROUP ANALYSES

Subgroup analyses for the primary outcome will evaluate the treatment effect across the following subgroups:

- 1) Received study product (plasma/saline) ≤ 7 days vs. >7 days after onset of symptoms
- 2) Have ≤ 2 vs. ≥ 3 comorbidities at baseline (age ≥ 65 years, underlying chronic lung, heart, kidney disease, hypertension, diabetes, obesity or immunosuppression)
- 3) Age <65 vs. ≥ 65
- 4) BMI <35 vs. ≥ 35

A forest plot will display point estimates and confidence intervals across subgroups. Interaction tests will be conducted to determine whether the treatment effect varies by subgroup. We may adjust for selected baseline covariates in the assessment of interactions. We anticipate that convalescent plasma has a larger benefit in those treated early (≤ 7 days after onset of symptoms), having more comorbidities at baseline, or older (≥ 65 years old), and a smaller benefit in obese individuals.

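### Obesity counts toward the comorbidity group expected to benefit more, although obese participants are expected to benefit less; if both expectations hold, the subgroup contrast is diluted

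*Combined protocol and SAP*

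**What the plan says.** Section 9.4.7 (printed 2.4.7) lists four subgroup analyses of the primary outcome. The second is defined as "Have ≤ 2 vs. ≥ 3 comorbidities at baseline (age ≥ 65 years, underlying chronic lung, heart, kidney disease, hypertension, diabetes, obesity or immunosuppression". The fourth cuts BMI at 35.

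The closing sentence gives the expected directions. More benefit is expected in participants "having more comorbidities at baseline, or older (≥ 65 years old", among others, "and a smaller benefit in obese individuals".

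The count is not confined to that section. Exploratory objective 2 in section 3, Table 2 uses "Primary outcome in persons with ≤ 2 or ≥ 3 comorbidities", with "chronic lung, cardiac and renal disease, hypertension, diabetes, obesity and immunosuppression" among the items. Section 8.3.5 repeats "cardiac and renal disease, hypertension, diabetes, obesity and immunosuppression".

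The only provision that bears on the two expectations is "We may adjust for selected baseline covariates in the assessment of interactions". It is optional and names no covariate. The count gives no BMI cut for obesity.

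**The concern.** One factor is used in two ways. It adds one to a count whose higher values are expected to mean more benefit, and it is itself expected to mean less benefit. A participant with obesity and exactly two other conditions is placed in the higher group by obesity alone. More generally, obese participants become concentrated in that group.

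What is at stake is the reading of exploratory objective 2, which asks whether the plasma effect differs by comorbidity. If the plan's own expectations are right, the contrast under test is smaller than the one produced by the other seven conditions. A small or null interaction could then mean that comorbidity does not modify the effect, or that two modifiers partly cancel. The listed count alone cannot separate these.

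**Working it through.** **Figures in the plan.** The documents give no sample size, power, prevalence or effect size for any subgroup contrast, so there is no subgroup figure to reproduce. The overall figure used below does reproduce with unpooled variance: (1.96 + 1.036)² × (0.30×0.70 + 0.20×0.80) / 0.10² ≈ 332, so 333 per arm and 666 in total, as in Table 6.

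**Assumptions (none from the documents).** The seven non-obesity items are independent, with prevalences 55, 25, 30, 20, 65, 40 and 8%. Obesity is independent of them, with prevalence 30, 40 or 50%. Let k be the number of non-obesity items. Absolute benefit rises 2.5 points per item and falls by a penalty d if the participant is obese.

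**Formula.** Contrast (≥3 minus ≤2) = 2.5 × (difference in mean k) − d × (difference in proportion obese).

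**Obesity left out of the count.** P(k ≥ 3) = 46.3%. Mean k is 3.468 in the higher group and 1.535 in the lower. Obesity is balanced by independence, so the contrast is 2.5 × 1.934 = 4.8 points for every d.

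**Obesity counted.** The share moved up by obesity alone is its prevalence × P(k = 2), with P(k = 2) = 32.35%.

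| Obesity prevalence | 30% | 40% | 50% |
|---|---|---|---|
| Moved into ≥3 group | 9.7% | 12.9% | 16.2% |
| Size of ≥3 group | 56% | 59% | 62% |
| Obese in ≥3 / ≤2 group | 42% / 15% | 53% / 21% | 63% / 28% |
| Difference in mean k | 1.782 | 1.761 | 1.754 |
| Difference in proportion obese | 0.276 | 0.322 | 0.345 |
| Contrast, d = 0 | 4.5 | 4.4 | 4.4 |
| Contrast, d = 3 | 3.6 | 3.4 | 3.4 |
| Contrast, d = 5 | 3.1 | 2.8 | 2.7 |
| Contrast, d = 8 | 2.2 | 1.8 | 1.6 |

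For example, at 40% and d = 8: 2.5 × 1.761 − 8 × 0.322 = 4.40 − 2.57 = 1.8 points.

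**Reversal.** The contrast reaches zero when d = 2.5 × (difference in mean k) / (difference in proportion obese): about 16, 14 and 13 points at the three prevalences.

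**A second shape.** Suppose benefit is 13 points with three or more non-obesity items and 7 otherwise, less the penalty. The contrast is 6.0 points without obesity. With obesity counted (30/40/50%) it is 4.4/4.0/3.8 for a 2-point penalty, 3.6/3.1/2.7 for 5 points and 2.2/1.5/1.0 for 10 points. The direction is the same.

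**Interaction power.** Assume equal halves of 666 and the planned 30% and 20% event rates for the variances. SE = √(2 × 0.37 / 166.5) = 6.7 points. At two-sided 0.05, power is about 11% for 4.8 points and about 15% for 6.0 points. For the 1.6-3.6 points seen with obesity counted, it is about 6-8%.

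**The case against.** A reader might infer that the plan contradicts itself, that the interaction test is biased, or that the contrast would come out reversed. The documents support none of these.

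- **Contradiction.** Obesity is one item of eight. Benefit can rise with total burden while obesity alone lowers it. The list largely follows the risk factors named in the protocol's introduction, so a burden count that includes obesity is a defensible choice.
- **Bias.** Exploratory objective 2 is non-directional and refers to a defined count. The test estimates the contrast for that count. Removing obesity asks a somewhat different question. The calculation above also favours the count without obesity by construction, because benefit is assumed to rise only with the other items.
- **Reversal.** It needs a penalty of about 13-16 points in the first model, more than the 10-point overall reduction the trial is planned on.

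Three further points stand. Part of the loss, about 0.4 points, appears with no penalty and has nothing to do with opposing expectations. Second, obesity in the count may not mean BMI ≥ 35. If only 40% of those counted as obese carried the penalty, penalties of 5-8 points would act like 2-3.2 points and leave about 3.3-3.9 points. Third, low power makes a null result uninformative under either definition.

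The separate BMI subgroup and the forest plot show an obesity effect directly, but they leave the comorbidity count mixed. Optional adjustment with no named covariates is not a planned safeguard.

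A reader might also see a conflict in age ≥ 65 being both a count item and its own subgroup. Both expectations point the same way there, so it is overlap and needs no change.

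**Conclusion.** The point holds as a matter of dilution and interpretability. If both of the plan's expectations are right, counting obesity shrinks the comorbidity contrast, and a small or null interaction has two explanations that the listed count cannot tell apart.

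The direction was the same in every scenario tried. The size is not in the documents. It rests on assumed prevalences, independence between conditions, the assumed gain per condition and the assumed penalty, so no single percentage loss should be quoted as a property of the trial.

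This is a minor, inexpensive improvement to an exploratory analysis. It does not touch the primary test, the sample size or the type I error.

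**What to change.** Before unblinding, do one of the following:

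1. Remove obesity from the comorbidity count in Table 2, section 8.3.5 and section 9.4.7. It keeps its own BMI subgroup.
2. Keep the listed count and pre-specify the same interaction analysis with obesity left out, reported beside it.

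The second is easier to defend, because it preserves the risk-factor count and shows whether obesity drives the result. If obesity stays in the count, state its BMI cut in the same edit. The statistical analysis plan, which section 9.4.1 (printed 2.4.1) says is still to be written, is a natural place for this.

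No new data are needed. The cost is one extra exploratory analysis, or a smaller ≥3 group under the first option (46% instead of 56-62% of participants under the assumptions above). Neither option makes the interaction test well powered.

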2.4.8 EXPLORATORY ANALYSES

We will explore if the treatment benefit of convalescent plasma differs by race (White vs. other races) and ethnicity (Hispanic vs. non-Hispanic), after adjusting for demographics (such as age, sex) and social economic status (such as highest attained educational level and income level) and if feasible, air-pollution data from geo-coding. We will also explore if the treatment benefit differs by ABO blood type.

3 SUPPORTING DOCUMENTATION AND OPERATIONAL CONSIDERATIONS

3.1 Regulatory, Ethical, and Study Oversight Considerations

3.1.1 INFORMED CONSENT PROCESS

3.1.1.1 CONSENT/ASSENT AND OTHER INFORMATIONAL DOCUMENTS PROVIDED TO PARTICIPANTS

Consent forms describing in detail the study intervention, study procedures, and risks will be given to the participant. Written documentation of informed consent is required prior to starting intervention/administering study interventions.

3.1.1.2 CONSENT PROCEDURES AND DOCUMENTATION

Informed consent is a process that is initiated prior to the prospective participant's agreeing to participate in the study and continues throughout the potential participant's study participation. The most current, CIRB-approved version of the consent form must be used.

The prospective participant will be informed of the rationale for the study, follow-up procedures that are required, and potential risks and benefits of participation. Prospective participants have the option of having family and/or anyone else they deem appropriate present during the informed consent process. The site personnel will verbally discuss the study and all elements of the informed consent document. The prospective participant and/or LAR will be informed that he/she may refuse to participate or withdraw from the study at any time without, in any way, jeopardizing his/her medical care or benefits in the VA system.

The prospective participant or LAR will be given the informed consent form and encouraged to carefully read and review the document and ask any and all questions. The site staff will address questions raised. The prospective participant is then given the opportunity to provide informed consent to participate in the study and to sign the Informed Consent Form. If the patient is unable to provide informed consent and there is a LAR, investigators should obtain consent from the patient's LAR. The Informed Consent Form can be signed on a hard copy or signed electronically via approved mechanisms.

If the prospective participant or LAR provides informed consent and signs the form, the original form is filed in the Subject Consent Forms Master File, a copy is sent to the Palo Alto CSPCC, a copy is filed per local site VA policy, and another copy is given to the patient or LAR. No research procedures may be performed prior to obtaining consent. In addition, each consented patient or LAR must sign a VA research HIPAA authorization (on a hard copy or electronically, if available).

Although the consenting process can be done in the patient's room, due to the nature of the risks of exposure to a COVID-19 patient, direct communication with the patient may not be feasible or safe. Accordingly, **the informed consent may be provided by video or phone:**

- Site personnel will obtain the patient's phone number (e.g. bedside phone or cell phone), and arrange a three-way call or video conference with the patient or LAR, an impartial witness, and if desired and feasible, additional persons requested by the patient or LAR (e.g., next of kin).

- To ensure that patients are approached in a consistent fashion, a standard process should be used when contacting the patient remotely that will accomplish the following:
 - Identification of who is on the call.
 - Review of the ICF with the patient by the site personnel and response to any questions the patient may have,
 - Confirmation by the witness that the patient's questions have been answered,
 - Confirmation by the site personnel that the patient is willing to participate in the trial and sign the informed consent document while the witness is listening on the phone,
 - Verbal confirmation by the patient that they would like to participate in the trial and that they have signed and dated the informed consent document that is in their possession.

If the patient/LAR signs a hard copy of the informed consent form, the signed informed consent document can be obtained by the following procedure and included in the study records:

- Full copy of the Informed Consent is provided to patient and/or LAR during consent for review that they keep.
- Signature page given to patient or LAR at the time of consent; the patient or LAR signs the consent using gloves and a pen that stay in the room.
- Signature page placed in a plastic zip-lock bag that is wiped with purple top wipe before leaving room and then again outside of room after provided with fresh gloves.
- Signature page can be scanned while in bag.
- Signature page removed and added to full consent after 1 week.
- Sites can also use UV if that is local procedure.

If a hard copy of signed informed consent document will not be able to be collected from the patient's location and included in the study records, the following two options are acceptable to provide documentation that the patient signed the informed consent document:

- **Option #1:** Attestations by the witness who participated in the call and by the site personnel that the participant or LAR confirmed that they agreed to participate in the study and signed the informed consent,

Please note: It is recommended that the documented verbal confirmation include information on the version of the IRB-approved informed consent document that was used, such as IRB-approval date and version.

- **Option #2:** A photograph of the informed consent document with attestation by the person entering the photograph into the study record that states how that photograph was obtained and that it is a photograph of the informed consent signed by the patient or LAR.

A copy of the informed consent document signed by the site personnel and witness should include a notation by the site personnel of how the consent was obtained, e.g. telephone, photograph, e-consent. The note should document how it was confirmed that the patient signed the ICF (i.e., either using attestation by the witness and investigator, the photograph of the

signed consent, or e-consent). If applicable, the note should include a statement of why the ICF signed by the patient was not retained, e.g., due to contamination of the document by infectious material.

Site personnel will send CSPC the informed consent document signed by the participant or LAR or obtained via one of the two options described above via netapp share folder within 30 days of consent.

Re-consent

Participants enrolled by their LAR must be consented for continued participation in study should they later become competent prior to day 29. The data and samples collected prior to the point when the participant declines to continue participation can be used in the analysis.

8.5.5 STUDY DISCONTINUATION AND CLOSURE

When a study is prematurely terminated, refer to **Section 7, Study Intervention Discontinuation and Participant Discontinuation/Withdrawal**, for handling of enrolled study participants.

This study may be suspended or prematurely terminated if there is sufficient reasonable cause. Written notification, documenting the reason for study suspension or termination, will be provided by the suspending or terminating party to study participants, investigator, funding agency, and regulatory authorities. If the study is prematurely terminated or suspended, the Study Chairs will promptly inform study participants, the VA CIRB, and sponsor and will provide the reason(s) for the termination or suspension. Study participants will be contacted, as applicable, and be informed of changes to study visit schedule.

Circumstances that may warrant termination or suspension include, but are not limited to:

- Determination of unexpected, significant, or unacceptable risk to participants;
- Demonstration of efficacy that would warrant stopping;
- Insufficient compliance to protocol requirements;
- Data that are not sufficiently complete and/or evaluable.

Study may resume once concerns about safety, protocol compliance, and data quality are addressed, and satisfy the sponsor and CIRB.

3.1.2 CONFIDENTIALITY AND PRIVACY

Participant confidentiality and privacy is strictly held in trust by the participating investigators, their staff, and the sponsor and their interventions. Therefore, the study protocol, documentation, data, and all other information generated will be held in strict confidence. No information concerning the study, or the data will be released to any unauthorized third party without prior written approval of the sponsor.

All research activities will be conducted in as private a setting as possible.

The study monitor, other authorized representatives of the sponsor, representatives of the CIRB, regulatory agencies or the Cooperative Studies Program Research Pharmacy Coordinating Center (CSPRPC) may inspect all documents and records required to be maintained by the investigator, including but not limited to, medical records (office, clinic, or

hospital) and pharmacy records for the participants in this study. The clinical study site will permit access to such records.

The study participant's contact information will be securely stored at each clinical site for internal use during the study. At the end of the study, all records will continue to be kept in a secure location for as long a period as dictated by the reviewing IRB, Institutional policies, or sponsor requirements.

Study participant research data, which is for purposes of statistical analysis and scientific reporting, will be transmitted to and stored at the Palo Alto Cooperative Studies Program Coordinating Center (CSPCC). This will not include the participant's contact or identifying information. Rather, individual participants and their research data will be identified by a unique study identification number. The study data entry and study management systems used by clinical sites and by CSPCC research staff will be secured and password protected. At the end of the study, all study databases will be de-identified and archived at the Palo Alto CSPCC.

3.1.3 FUTURE USE OF STORED SPECIMENS AND DATA

*See also **Section 10.1.3, Confidentiality and Privacy** and **Section 10.1.11, Data Handling and Record Keeping**, for further information on future use of study records.*

Data collected for this study will be analyzed and stored at the Palo Alto Cooperative Studies Program Coordinating Center (CSPCC). After the study is completed, the de-identified, archived data will continue to be stored at the Palo Alto CSPCC, accessible for use by researchers including those outside of the study with an approved Data Use Agreement. The biospecimens collected in the study for current and future research will be kept at the Cooperative Studies Program Albuquerque Central Biorepository in Albuquerque, NM unless otherwise specified. All stored specimens and data used for current and future experimental analysis, both clinical and laboratory, by laboratories and investigators within and outside the VA system will be linked to study identification number with no direct subject identifiers or PII/PHI. Thus, all subject data will be deidentified and anonymized with demographic but no specific HIPAA-designated variables. The biospecimens will be accessible for future research with an approved Sample Use Agreement. The VA CIRB will oversee the biorepository for this study. All samples will be destroyed by standard practice within 20 years of study completion. Sample destruction will be validated according to the Standard Operating Procedures of the VA Biorepository.

